1. LIST OF ABBREVIATIONS

Term	Definition / description
AE	Adverse event
ADR	Adverse Drug Reaction
ANOVA	Analysis of Variance
BMI	Body Mass Index
CRF	Case report form
CKD	Chronic Kidney Disease
DBLM	Database lock meeting
eGFR	Estimated Glomerular Filtration Rate
FAS	Full Analysis Set
HbA1c	Glycated Haemoglobin A1c
ICH	International Conference on Harmonisation
MedDRA	Medical Dictionary for Regulatory Activities
NSP	Non-interventional Study Protocol
PT	Preferred term
PV	Protocol violation
Q1	Lower quartile
Q3	Upper quartile
RPM	Report planning meeting
SD	Standard deviation
SEAP	Statistical and Epidemiological Analysis Plan
SOC	System organ class
T2DM	Type 2 Diabetes Mellitus

2. INTRODUCTION

As per International Conference on Harmonisation (ICH) guideline E9, the purpose of this document is to provide a more technical and detailed elaboration of the principal features of the analysis described in the protocol, and to include detailed procedures for executing the statistical analysis of the primary and secondary variables and other data.

This Statistical and Epidemiological Analysis Plan (SEAP) assumes familiarity with the Non-interventional Study Protocol (NSP). In particular, the SEAP is based on the planned analysis specification as written in NSP Section 9 “Research Methods”. Therefore, SEAP readers may consult the NSP for more background information on the study, e.g., on study objectives, study design and population, treatments, definition of measurements and variables, planning of sample size.

3. CHANGES IN THE PLANNED ANALYSIS OF THE STUDY

Three additional further outcomes (Hyperuricemia, Hypercholesteremia and Hypertriglyceridemia) are identified from the lab test results, and collected on eCRF, due to the consideration that missing values of lab tests results are inevitable and those diagnosis/diseases are more interested outcomes. In the analyses, they will be considered as part of medical history.

The analysis population Full Analysis Set (FAS), which includes all patients with an HbA1c measurement, is modified to: Full Analysis Set – Eligible (FAS – E), which includes all eligible patients regarding to inclusion and exclusion criteria with an HbA1c measurement.

Two additional sets, FAS – E with Hypoglycaemia and FAS – E with Hypoglycaemia leading to therapy change, are created for the analysis of treatment pattern.

5. OUTCOMES

5.1 MAIN OUTCOMES

The primary outcome is the proportion of patients attaining blood glucose control target of HbA1c<7%.

NSP 9.3.2 defines the following parameters as secondary outcomes:

- Renal function level of patients
- Treatment regimens for T2DM that patient are currently taking
- Proportion of macro-vascular and micro-vascular diabetic complications
- Proportion of Hypoglycaemic occurrence
- Proportion of Hypoglycaemia leading to therapy change
- Proportion of Anti-hypertension therapy usage
- Proportion of Lipid Lowering therapy usage
- Proportion of Anti-Platelet therapy usage
- Treatment adherence to Chinese T2DM guideline 2013

5.3 OTHER VARIABLES

All adverse drug reactions (ADRs) (serious and non-serious) and all AEs with fatal outcome (death) for any BI drug approved for the indication of T2DM must be collected by the investigator from signing the informed consent onwards until the end of the study.

6. GENERAL ANALYSIS DEFINITIONS

6.1 EXPOSURE

Not applicable.

6.2 IMPORTANT PROTOCOL VIOLATIONS

Not applicable.

6.3 PATIENT SETS ANALYSED

- Full Analysis Set – Eligible (FAS – E):
The FAS – E includes all eligible patients regarding to inclusion and exclusion criteria with an HbA1c measurement.
- FAS – Albuminuria:
The FAS – Albuminuria dataset is a subset of patients of FAS – E, which includes T2DM patients with albuminuria (micro-albuminuria without urinary tract infection based on urine WBC result and macro-albuminuria).
- FAS – E with Hypoglycaemia:
The FAS – E with Hypoglycaemia dataset is a subset of patients of FAS – E, which includes T2DM patients with Hypoglycaemia as medical history.
- FAS – E with Hypoglycaemia leading to therapy change:
The FAS – E with Hypoglycaemia leading to therapy change dataset is a subset of patients of FAS – E, which includes T2DM patients with Hypoglycaemia leading to therapy change as medical history.

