9.5 STUDY SIZE

According to a recent study, the proportion of patients with diabetes in China who achieved a target blood glucose level of HbA_{1c} <7% was 39.8% in patients aged 60-69 years old and 38.9% in patients aged 70 years old or above ^[1]. It is assumed that the proportion of patients

attaining the target blood glucose level in the present study will be 39%. To ensure the accuracy of the estimate for proportion of patients with $HbA_{1c} < 7\%$, the length of a two-sided 95% confidence interval (CI) should not extend beyond 5%. A sample size of 1463 patients is required to achieve the expected accuracy. Assuming HbA_{1c} measurements are available for 97.5% of the enrolled patients, a total of 1500 patients will be recruited.

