9.7.1 Analysis population

The statistical analysis will be based on the following populations.

Full Analysis Set (FAS)

The FAS includes all patients with an HbA_{1c} measurement.

FAS – Albuminuria

The FAS – Albuminuria dataset is a subset of patients of FAS, which includes T2DM patients with albuminuria (micro-albuminuria without urinary tract infection based on urine WBC result and macro- albuminuria).

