9.7.3 Secondary analyses

The analyses for following secondary outcomes will be performed on both FAS and FAS - Albuminuria as below:

- For renal function variables, eGFR and albuminuria, descriptive statistics will be calculated
- The treatment pattern for T2DM will be summarized descriptively with frequency and proportion,
- The proportion of the occurrence of hypoglycaemia and the proportion of hypoglycaemia leading to therapy change will be summarized descriptively.

Then for the other secondary outcomes, the analyses will only be performed on FAS:

- The proportion of each macro vascular and micro-vascular diabetic complications will be calculated.
- The proportion of using anti-hypertension therapy, lipid –lowering therapy, and anti-platelet therapy will be calculated respectively.
- The treatment adherence will be summarized using the proportion of each follow-up duration category.

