6.5 HANDLING OF MISSING DATA AND OUTLIERS

If patients have missing values for an outcome, those patients will be excluded for that outcome's analysis. No imputation approach will be applied. Any removal from the analysis will be documented.

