7.6 MAIN ANALYSES

The blood glucose control proportion (HbA1c<7%) will be tabulated on FAS – E.

The analyses for parameters below will be performed on both FAS – E and FAS – Albuminuria:

- Renal function variables (eGFR, albuminuria, and CKD staging) will be summarized
- The proportion of the occurrence of hypoglycaemia and the proportion of hypoglycaemia leading to therapy change will be summarized descriptively.

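### Secondary outcomes and adverse event summaries are limited to patients with an HbA1c value that none of them needs; the expected effect is small and the remedy is cheap

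*SAP*

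**What the plan says.** The condition starts in the protocol. Section 9.7.1 states: "The FAS includes all patients with an HbA_{1c} measurement". Section 9.7.3 then assigns the secondary outcomes in two groups.

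- For renal function, diabetes treatment pattern and hypoglycaemia: "The analyses for following secondary outcomes will be performed on both FAS and FAS - Albuminuria as below".
- For complications, blood-pressure, lipid and antiplatelet treatment, and adherence: "Then for the other secondary outcomes, the analyses will only be performed on FAS".

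SAP section 3 adds eligibility to the definition and keeps the HbA1c requirement. SAP 6.3 reads: "The FAS – E includes all eligible patients regarding to inclusion and exclusion criteria with an HbA1c measurement". The albuminuria set and both hypoglycaemia sets are carved out of it, for example: "The FAS – E with Hypoglycaemia dataset is a subset of patients of FAS – E".

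The SAP uses these sets wherever it names one: in 7.1 for baseline characteristics and adherence, in 7.2 for treatment pattern, in 7.6 for renal function and hypoglycaemia ("The analyses for parameters below will be performed on both FAS – E and FAS – Albuminuria"), and in 7.9.1 for adverse events. SAP 7.2 names no set for complications or co-treatments, so for those the restriction comes from protocol 9.7.3.

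On missing values, SAP 6.5 says: "If patients have missing values for an outcome, those patients will be excluded". The exclusion applies to the analysis of the outcome concerned, without imputation, and any removal has to be documented.

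**The concern.** Renal function, regimen, complications, hypoglycaemia, co-treatment and adherence can all be recorded for a patient who has no HbA1c result. Under the set definitions, one missing laboratory value removes that patient from all of these tables. SAP 6.5 suggests a different intent, namely that a gap costs a patient only the analysis in which the gap lies. SAP section 3 itself accepts that laboratory values will be missing.

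Two things are at stake.

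- The secondary objectives in protocol section 8 concern the study population, but the tables would describe only those in whom HbA1c was obtained.
- Adverse drug reactions and deaths on the sponsor's diabetes drugs are to be collected from consent onwards (protocol 9.3.4 and 11.2, SAP 5.3). Such an event in a patient without HbA1c would be absent from the summaries in SAP 7.9.1.

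Missing HbA1c is possible under the visit rules. Protocol 9.2.2 asks for laboratory tests on the visit day. It allows earlier results for fasting glucose (one month) and for creatinine, uric acid and lipids (three months), but states no such window for HbA1c.

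**Working it through.** **1. Reproduce the plan's figures.** Inputs from protocol 9.5 are an expected proportion of 39%, a two-sided 95% interval of full width 5 points, and the assumption that "measurements are available for 97.5% of the enrolled patients".

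- n = (1.96 / 0.025)² × 0.39 × 0.61 = 1462.2, rounded up to 1463. This matches the protocol. Reading 5% as the half-width would give 366, so full width is meant.
- Enrolment: 1463 / 0.975 = 1500.5, against 1500 stated. The difference is only rounding.

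**2. Patients left out at the planned availability.** 1500 − 1463 = 37, or 2.5% of those enrolled. This treats all 1500 as eligible.

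**3. Precision.** Width = 2 × 1.96 × √(p(1 − p)/n).

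- At p = 39%: 5.00 points with the restriction, 4.94 with all 1500.
- At p = 50%: 5.12 points against 5.06.
- The ratio is √(1500/1463) = 1.013, so intervals are about 1.3% wider for any proportion.

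**4. Bias.** Let m be the share without HbA1c. The proportion in all eligible patients is (1 − m) × p(with) + m × p(without). The restricted estimate is p(with). Its bias is therefore m × [p(with) − p(without)]. The documents give only m = 2.5%; the other values of m and all the differences are assumptions.

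| Share without HbA1c | Patients left out | Interval width ratio | Bias at 10 / 20 / 30 points difference |
|---|---|---|---|
| 2.5% (plan) | about 37 | 1.013 | 0.25 / 0.5 / 0.75 points |
| 5% (assumption) | 75 | 1.026 | 0.5 / 1.0 / 1.5 points |
| 10% (assumption) | 150 | 1.054 | 1 / 2 / 3 points |

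At 2.5% missing the bias cannot exceed 2.5 points (0.025 × 100).

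**5. Does any outcome need HbA1c?** None of the secondary outcomes in protocol 9.3.2 or SAP 5.1 is defined by it. One secondary objective in protocol section 8 does need it: blood glucose control in patients with albuminuria. It is not a listed secondary outcome.

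**The case against.** The strongest case for the plan has four parts.

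- **No rule is broken.** A reader might infer that SAP 6.3 violates SAP 6.5. The text does not support that. Section 6.3 settles who is in a set, and 6.5 can be read as applying within it. This stands: the two are in tension, not in contradiction.
- **It is a protocol decision.** The condition comes from protocol 9.7.1 and 9.7.3; the SAP added only eligibility. This also stands, and it means that a change departs from the protocol and has to be recorded as such.
- **Nothing is lost from view.** A reader might infer that the data are discarded. The documents say only who enters the summaries. SAP 6.5 requires removals to be documented, and SAP 7.9.5 reports disposition. So the data are left out of the tables, not deleted.
- **A common denominator is useful.** It lets regimen, renal and hypoglycaemia profiles describe the same patients as the HbA1c result, in a study that protocol 9.7 calls exploratory. This is a legitimate choice, but the documents do not give it as the reason, and it does not explain restricting the adverse event tables.

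It is also tempting to say that missing HbA1c will cluster in certain hospitals or in frailer patients. Nothing in the documents shows this. Urine albumin and urine white cells are visit-day tests too, so a patient without HbA1c may lack them as well. Fewer than 37 might then be regained for albuminuria.

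**Conclusion.** The restriction is real, covers every listed secondary outcome and the adverse event summaries, and is unexplained. On the plan's own 97.5% availability its expected effect is small: about 37 of 1500 patients, about 1.3% in interval width, and about 0.5 points of bias under an assumed 20-point difference, against a planned interval width of 5 points. A reader might infer materially biased secondary results. That would require HbA1c to be missing much more often than planned, or missingness to be strongly related to the outcomes. The 2-point figure needs both 10% missing and a 20-point difference, and neither is in the documents. The 97.5% is itself only a planning assumption, so the number without HbA1c should be reported whatever is decided. The adverse event point does not depend on these percentages, because a single reportable reaction or death could be missing from the tables. Overall this is a cheap improvement, not a serious defect.

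**What to change.** In SAP 6.3, define a set of all eligible consented patients, with or without HbA1c. Then:

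- Use it for secondary outcomes that do not involve HbA1c, for the albuminuria and hypoglycaemia subsets of those outcomes, and for the adverse event summaries in SAP 7.9.1. Name the set in SAP 7.2 for complications and co-treatments.
- Keep FAS-E for the proportion below 7%, its subgroups and the logistic model.
- Keep an HbA1c-restricted albuminuria subset for glucose control in patients with albuminuria.
- Apply SAP 6.5 outcome by outcome within the new set.
- Record the change in SAP section 3 as a departure from protocol 9.7.1 and 9.7.3.
- Report how many eligible patients lack HbA1c, and print N in each table.

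No additional data are needed. The cost is SAP wording, denominators that differ between primary and secondary tables, and one additional albuminuria subset.

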6.5 HANDLING OF MISSING DATA AND OUTLIERS

If patients have missing values for an outcome, those patients will be excluded for that outcome's analysis. No imputation approach will be applied. Any removal from the analysis will be documented.

6.6 BASELINE, TIME WINDOWS AND CALCULATED VISITS

Not applicable.

7. PLANNED ANALYSIS

The following standard descriptive statistical parameters will be displayed in summary tables of all continuous variables:

N	number of non-missing observations
Mean	arithmetic mean
SD	standard deviation
Min	minimum
Median	median
Max	maximum

Tabulations of frequencies for categorical data will include all possible categories and will display the number of observations in a category as well as the percentage (%) relative to the respective treatment group (unless otherwise specified, all subjects in the respective subject set whether they have non-missing values or not). Percentages will be rounded to one decimal place. The category missing will be displayed only if there are actually missing values.

For logistic regression model, adjusted odds ratio with 95% confidence interval, and p-value will be provided for the factors involved.

All data processing, summarization and analyses will be performed using Version 9.2 (or later) of the SAS statistical software package (Windows OS).

7.1 DEMOGRAPHIC AND OTHER BASELINE CHARACTERISTICS

Summary statistics will be provided for the following demographics and baseline characteristics: Age, Age category, Gender, Education level, Smoking history, Physical activity, Body height, Body weight, BMI, Waist circumference, Heart rate, Systolic blood pressure, Diastolic blood pressure, Medical history, Treatment adherence to Chinese T2DM guideline 2013, Family history, Follow-up duration and Albuminuria. Descriptive statistics will be presented for continuous variables. Frequency and proportion will be used to summarize categorical variables. These will be based on both FAS – E and FAS – Albuminuria.

By-subject listings will be produced accordingly.

7.2 CONCOMITANT DISEASES AND MEDICATION

The treatment pattern for T2DM will be summarized descriptively with frequency and proportion on FAS – E, FAS – E with Hypoglycaemia, FAS – E with Hypoglycaemia leading to therapy change, and FAS – Albuminuria.

The proportion of using anti-hypertension therapy, lipid-lowering therapy, and antiplatelet therapy will be calculated respectively. The concomitant medications will be coded according to the most recent version of the World Health Organization – Drug Dictionary

Proprietary confidential information © 2018 Boehringer Ingelheim International GmbH or one or more of its affiliated companies

Enhanced/Herbal Dictionary (WHO DDE/HD), and summarized by ATC level 4 and preferred term.

The proportion of each macro-vascular and micro-vascular diabetic complication will be summarized respectively.

By-subject listings will be produced accordingly.

7.3 METHODS ADDRESSING BIAS

Not applicable.

7.4 METHODS ADDRESSING CONFOUNDING / EFFECT MEASURE MODIFICATION

Identified confounders will be included in the logistic regression model to adjust the main outcome result. However unidentified confounders cannot be controlled for using statistical analyses.

7.6 MAIN ANALYSES

The blood glucose control proportion (HbA1c<7%) will be tabulated on FAS – E.

The analyses for parameters below will be performed on both FAS – E and FAS – Albuminuria:

- Renal function variables (eGFR, albuminuria, and CKD staging) will be summarized
- The proportion of the occurrence of hypoglycaemia and the proportion of hypoglycaemia leading to therapy change will be summarized descriptively.

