8. RESEARCH QUESTION AND OBJECTIVES

The present study is to be conducted in older (≥ 60 years old) outpatients with T2DM in hospitals of China.

The primary objective is:

- to assess the level of blood glucose, measured by the proportion of patients attaining the blood glucose control target defined as $HbA_{1c} < 7\%$.

The secondary objectives are:

- to investigate the anti-hyperglycaemic treatment patterns of the study population.
- to investigate occurrence of the hypoglycaemia and hypoglycaemia leading to therapy change.
- to investigate the anti-hypertension/Lipid Lowering/anti-platelet treatment patterns of the study population.
- to investigate treatment adherence (follow up duration) to Chinese T2DM guideline 2013
- to investigate the clinical characteristics of the study population.
- to investigate clinical characteristics, anti-hyperglycaemic treatment pattern and blood glucose control in older T2DM patients with albuminuria.

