9.7.2 Primary analyses

The proportion of patients attaining blood glucose control target of $HbA_{1c} < 7\%$ will be summarized descriptively on FAS.

Detailed information about variable categorization will be specified in SEAP.

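### Is HbA1c<7% in patients with albuminuria, part of a secondary objective, left without an analysis?

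*SAP*

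**What the plan says.** Protocol section 8 lists a secondary objective with three parts, all in older patients with albuminuria: clinical characteristics, anti-hyperglycaemic treatment pattern, and "blood glucose control in older T2DM patients with albuminuria".

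For the HbA1c<7% proportion, protocol 9.7.2 says that it "will be summarized descriptively on FAS". SAP section 3 narrows FAS to eligible patients (FAS-E), and SAP 7.6 says "The blood glucose control proportion (HbA1c<7%) will be tabulated on FAS – E".

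Separate text sets out what is run on both sets. Protocol 9.7.3 says "The analyses for following secondary outcomes will be performed on both FAS and FAS - Albuminuria as below" and names renal function, T2DM treatment pattern and hypoglycaemia. It continues "Then for the other secondary outcomes, the analyses will only be performed on FAS" for complications, the three co-therapies and treatment adherence. SAP 7.6 says "The analyses for parameters below will be performed on both FAS – E and FAS – Albuminuria" and names renal function and hypoglycaemia. HbA1c<7% is in none of these lists.

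The other two parts of the objective are covered. On demographics and baseline characteristics, SAP 7.1 says "These will be based on both FAS – E and FAS – Albuminuria". On treatment pattern, the sets named in SAP 7.2 end with "FAS – E with Hypoglycaemia leading to therapy change, and FAS – Albuminuria".

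**The concern.** Two of the three parts of the albuminuria objective can be traced to FAS-Albuminuria, and the third cannot. SAP 7.6 sharpens the contrast: one sentence puts HbA1c<7% on FAS-E, and the next opens a list for both sets that omits it. A programmer working from those lines alone would produce the proportion once, on FAS-E.

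The missing number would matter. The study title refers to patients with or without albuminuria. Protocol section 7 says that China has no data on patients who have both T2DM and albuminuria, and gives understanding glucose control with or without albuminuria as a purpose of the study. If the proportion at target in that group were never reported, a stated objective would go unanswered. The primary result would not be affected.

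**Working it through.** **1. The plan's own figure.** Protocol 9.5 gives p = 39% and a two-sided 95% interval of full length 5 points, so the half-width is 2.5 points.

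- n = z² × p(1 − p) / (half-width)², with z = 1.96 to two decimals. The unrounded z gives 1462.2, rounded up to **1,463**, as stated.
- Recruitment: 1,463 / 0.975 = 1,500.5, against 1,500 stated. Conversely, 1,500 × 0.975 = 1,462.5.

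The stated size reproduces. The question here is about analysis sets and changes none of these figures.

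**2. What is announced, against what can be read.**

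| Announced | Where | Readable specification |
|---|---|---|
| HbA1c<7% by demographic and clinical subgroups | Protocol abstract, data analysis | None in 9.7.2, 9.7.3 or SAP 7.6 |
| Logistic regression for glucose control | Protocol abstract; reporting format in SAP 7; adjustment in SAP 7.4 | No readable section specifies the model |
| Stratified analyses and confounding adjustment, answered yes with reference to 9.7 | ENCePP checklist, items 10.3 and 10.4 | None in the readable part of 9.7 |
| Laboratory data, referred to SAP 7.7 | SAP 7.9.2 | SAP goes from 7.6 to 7.8 |
| Further outcomes, three of them added | SAP section 3 | SAP goes from 5.1 to 5.3 |

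The protocol's table of contents also has blank entries after 9.3.2 and after 9.7.3, and the amendment log confirms that a section 9.3.3 existed. More HbA1c<7% analyses are planned than can be read, and the gaps fall where such analyses would be described. HbA1c is itself a laboratory test in protocol 9.2.2, so the SAP 7.9.2 reference to 7.7 is one possible route to it. SAP 7.1 lists albuminuria as a baseline characteristic, which makes it an obvious candidate for the subgroup tables.

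**3. Can the result be produced from what is defined?** FAS-Albuminuria is a subset of FAS-E (SAP 6.3), and FAS-E requires an HbA1c measurement. Every member therefore has the value. No new set, data or missing-data rule is needed.

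**4. Precision of that result (illustration).** Half-width = 1.96 × √(0.39 × 0.61 / n), assuming simple random sampling and the same 39%. The 26.1% is the Shanghai figure in protocol section 7, not a planning input. The other prevalences and the urinary-infection exclusions are assumptions.

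| Case | n | 95% half-width (points) |
|---|---|---|
| All of FAS-E | 1,463 | 2.5 |
| 26.1% with albuminuria | 0.261 × 1,463 = 382 | 4.9 |
| 26.1%, 10% of them excluded for infection | 0.9 × 0.261 × 1,463 = 344 | 5.2 |
| 26.1%, 20% of them excluded | 0.8 × 0.261 × 1,463 = 305 | 5.5 |
| 15% with albuminuria | 219 | 6.5 |
| 40% with albuminuria | 585 | 4.0 |

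These figures show that a subset proportion would be usable for description. They do not measure any defect, because the readable text does not establish one.

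**The case for a change.** The strongest argument for a change is traceability. A secondary objective should lead to its analysis from the section that specifies secondary analyses, whatever the withheld text contains. One added sentence or cross-reference in SAP 7.6 would be cheap. The abstract's subgroup tables are not a sure substitute, since they name neither albuminuria nor FAS-Albuminuria. A split by the categories in protocol Table 1 would also use a different denominator, because FAS-Albuminuria drops micro-albuminuria with urinary tract infection. Nor is it enough that some secondary outcomes are confined to FAS: those are not named individually in the albuminuria objective, and glucose control is.

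Much of this stands. The readable lists do omit the item, and the difference in denominator is real. But a difference in denominator does not leave the objective unanswered, and placing a subset result outside the main-analyses section is an acceptable layout. The argument for a change needs the result to be absent from the whole plan. With SAP 7.7 and the protocol entry after 9.7.3 unseen, that cannot be shown. A protocol edit would also cost more than a sentence, because protocol 9.10.2 makes amendments subject to ethics and competent-authority approval.

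**Conclusion.** No change follows. The mismatch in the readable text is real, but it is a question of where a result is located and does not show that an analysis is missing. The objective is written down, the analysis set exists, all its members have the measurement, and the documents announce further HbA1c<7% analyses whose specification is not public. An analyst with the full documents would either find the tabulation or produce it as a matter of course from the objective and the defined set.

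The primary proportion, its ±2.5-point precision and the sample size are untouched. The effect of an omission, if there were one, cannot be computed from the documents. The subset result would have a half-width of about ±4.9 points at the 26.1% background prevalence, and ±6.5 to ±4.0 over an assumed 15% to 40%.

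This conclusion rests on the withheld sections holding at least some of the HbA1c analyses that the abstract announces. A query to the sponsor about where the FAS-Albuminuria result is reported would settle it. Only if the answer were that it is reported nowhere would there be a gap, and SAP section 3 already exists to record an added tabulation.
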